14.3 Causality

Causal relationship will be assessed for IMPs, other trial treatments (nIMPs) and procedures:

Table 8: IMPs

AZD7442 (Combination Monoclonal Antibody Product) Comirnaty bivalent (Original/Omicron BA.1) vaccine (Pfizer BioNTech) Spikevax bivalent (Original/Omicron) vaccine (Moderna)

The Principal Investigator (or another delegated medically qualified doctor from the trial team) and Chief Investigator (or another medically qualified doctor from the Trial Management Group) will assess each SAE to determine the causal relationship:

Table 9: Causality assessment

Relationship	Description	that t	nable he SAE caused	may l	have
Unrelated	There is no evidence of any causal relationship with the trial/intervention	No			
Unlikely	There is little evidence to suggest there is a causal relationship with the trial/intervention (e.g. the event did not occur within a reasonable time after administration of the trial medication). There is another reasonable explanation for the event (e.g. the participant's clinical condition, other concomitant treatment).	No			
Possible	There is some evidence to suggest a causal relationship with the trial/intervention (e.g. because the event occurs within a reasonable time after administration of the trial medication). However, the influence of other factors may have contributed to the event (e.g. the	Yes			

	participant's clinical condition, other concomitant treatments).	
Probable	There is evidence to suggest a causal relationship and the influence of other factors is unlikely.	Yes
Definite	There is clear evidence to suggest a causal relationship and other possible contributing factors can be ruled out.	Yes

The causality assessment given by the Principal Investigator (or delegate) cannot be downgraded by the Chief Investigator (or delegate), and in the case of disagreement both opinions will be provided.

14.4 Expectedness

The Chief Investigator (or another delegated appropriately qualified individual) will assess each SAR to perform the assessment of expectedness.

The expectedness assessment should be made with reference to the current Reference Safety Information (RSI) for each IMP. Expectedness decisions must be based purely on whether the event is listed in the RSI; other factors such as the participant population and participant history should not be taken into account. Expectedness is not related to what is an anticipated event within a particular disease. SARs which add significant information on specificity or severity of a known, already documented adverse event constitute unexpected events. Fatal and life-threatening (LT) SARs should not be considered expected (unless explicitly stated in the RSI and approved by the NCA). For example, an event more specific or more severe than that described in the RSI is considered unexpected.

IMP	RSI to be used for expectedness assessment	Relevant section to be used for expectedness assessment
AZD7442 (Evusheld)	IB, AstraZeneca	Section 5.6
Comirnaty bivalent (Original/Omicron BA.1)	Pfizer SPC/BioNTech – bivalent vaccine Comirnaty Original/Omicron BA.1	Section 4.8
Spikevax bivalent Original/Omicron	Spikevax bivalent SPC	Section 4.8

Table 10: list of sources of RSI for each IMP.

Reference Safety Information (RSI) on any CTR trial will be reviewed regularly according to CTR procedures.

14.5 Reporting procedures

14.5.1 Participating Site Responsibilities

The PI (or delegated medically qualified doctor from the trial team) should sign and date the SAE CRF to acknowledge that he/she has performed the seriousness and causality assessments. Investigators should also report SAEs to their own health boards or trust in accordance with local practice.

A completed SAE form for all events requiring immediate reporting should be submitted via fax or email to the CTR within 24 hours of knowledge of the event. A separate form must be used to report each event, irrespective of whether or not the events had the same date of onset.

The participant will be identified only by trial number and year of birth. The participant's name (or any other personal identifiers) should not be used on any correspondence.

It is also required that sites respond to and clarify any queries raised on any reported SAEs and report any additional information as and when it becomes available through to the resolution of the event. Additionally, CTR/pharmaceutical companies may request additional information relating to any SAEs/SARs and the site should provide as much information as is available to them in order to resolve these queries.

Serious Adverse Event (SAE) email address:

[contact]

SAE [contact]

Serious adverse events should be reported from time of signature of informed consent, throughout the treatment period up to, and including 28 days after the participant receives their last dose of the IMP. Serious adverse reactions (such as long term side effects of trial treatment under investigation) should continue to be reported until the end of follow up as defined in the protocol.

Serious Adverse events (SAE) should be graded using the NCI Common Terminology Criteria for Adverse Events (CTCAE) Version 5.

An SAE form should contain at least the minimum information:

- Full participant trial number
- An Adverse Event / Adverse Reaction

• IMP or trial intervention

RDIF

• A completed assessment of the seriousness, and causality as performed by the PI (or another appropriately medically qualified doctor registered on the delegation log)

If any of these details are missing, the site will be contacted and the information must be provided by the site to the CTR within 24 hours.

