- All AEs reported were mild in intensity, with the exception of the following events of moderate intensity: urinary tract infection (1 subject) in Cohort 1a; headache, malaise (1 subject each) and urinary tract infection (1 subject) in Cohort 1b; dysmenorrhea and headache (1 subject each) and toothache (2 participants) in Cohort 2; headache, back pain, and arthralgia (1 subject each) in Cohort 3; and back pain (1 subject) in Cohort 4.
- There were no haematology, clinical chemistry, or vital signs findings of concern in any subject.

In addition, by Day 211, no participants in the study tested positive for ADA to either AZD8895 or AZD1061. Since ADA-positive to AZD7442 is defined as having a positive result to AZD8895 and/or AZD1061, no participants tested positive for ADA to AZD7442. Thus, both ADA prevalence (percentage

ARDIF

of ADA-positive participants in the study) and ADA incidence (percentage of treatment-emergent ADApositive participants in the study) were 0%. The serum AZD8895 and AZD1061 concentrations observed in the Phase I study support that the PK of the 2 antibodies are similar. The half-life of AZD7442 is estimated to be ~ 90 days which will allow for long-term protection. Overall, the Cmax and AUC increased linearly with increasing IV dose. Administering AZD8895 and AZD1061 separately or together did not alter the PK of the mAbs as indicated by the overlapping serum drug concentrationtime curves. In addition, key exposure PK parameters such as AUC and Cmax for AZD8895 and AZD1061 were similar between the 2 dosing regimens.

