4.7.1 Hypotheses to be tested

1) That treatment with AZD7442 in combination with a SARS-CoV-2 vaccine is safe and well tolerated,

2) That vaccination with a SARS-CoV-2 vaccine does not reduce AZD7442 titres in humans and

3) That AZD7442 in combination with a SARS-CoV-2 vaccine enhances immune responses to SARS-CoV-2.

5 Trial objectives/endpoints and outcome measures

We propose to test the following objectives:

Table 1: Objectives and outcome measures

	Objectives	Outcome measures
Co-Primary	To assess the pharmacokinetics of AZD7442 administered as a single dose of 600 mg IM in immunosuppressed patients	Serum samples will be taken at Day 0 (Predose AZD7442), and days 28, 112 and 180 post AZD7442 treatment and samples shipped to an AstraZeneca approved laboratory for Pharmacokinetics (PK) analysis.
		Samples collected for analyses of AZD7442 serum concentration may also be used to evaluate safety or efficacy aspects related to concerns arising during or after the trial. PK results from the trial will be compared to results from other phase III studies with AZD7442 such as PROVENT.
	To assess the safety and tolerability of a single IM dose of AZD7442, followed by SARS-CoV2 vaccine booster 28 days later with reference to serious adverse events (SAEs) in highly vulnerable patients.	SAE reporting throughout the trial using CTCAE V5.0
	To assess the SARS-CoV-2 specific humoral and cellular immune response against SARS-CoV-2 variants, when a SARS-CoV-2 vaccine is administered 28 days after AZD7442 in patients who are immune suppressed.	The function and magnitude of SARS-CoV-2 specific antibody and T cell responses will be measured at baseline and at additional multiple timepoints after the administration of AZD7442.
		Assays will quantify the amount of serum antibodies to the spike (S) and the nucleocapsid (N) antigens of SARS-CoV-2. This assay will enable the discrimination of antibody responses to SARS-CoV-2 that results from vaccination and/or SARS-CoV- 2 infection. Ab function, including viral neutralisation will be assessed.

		The magnitude and function of SARS-CoV-2 specific T cell responses following the booster vaccination will use assays that give insight into T cell function. Laboratories will measure neutralizing antibodies to SARS-CoV-2 using validated wild-type neutralization assay or pseudo- neutralization assays.

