14.1 Definitions

Table 7: definitions of pharmacovigilance terms

Term	Definition				
Adverse Event (AE)	Any untoward medical occurrence in a participant or clinical trial participant administered a medicinal product and which are not necessarily caused by or related to that product				
Adverse Reaction (AR)	Any untoward and unintended response in a clinical trial participant to an investigational medicinal product which is related to any dose administered to that participant				
Serious Adverse Event (SAE)	 Any adverse event that – 1. Results in death 2. Is life-threatening* 3. Required hospitalisation or prolongation of existing hospitalisation** 4. Results in persistent or significant disability or incapacity 5. Consists of a congenital anomaly or birth defect 6. Other medically important condition*** 				
Serious Adverse Reactions (SARs)	Any SAE occurring in a clinical trial participant for which there is a reasonable possibility that it is related to the IMP at any dose administered.				
Suspected Unexpected Serious Adverse Reactions (SUSARs)	A SAR, the nature and severity of which is not consistent with the Reference Safety Information (RSI) for the IMP.				

*Note: The term 'life-threatening' in the definition of serious refers to an event in which the trial participant was at risk of death at the time of the event or it is suspected that use or continued use of the product would result in the participants death; it does not refer to an event which hypothetically might have caused death if it were more severe.

**** Note:** Hospitalisation is defined as an inpatient admission, regardless of the length of stay, even if the hospitalisation is a precautionary measure for continued observation. Pre-planned hospitalisation e.g. for pre-existing conditions which have not worsened, or elective procedures, does not constitute an SAE.

******* Note: other events that may not result in death, are not life-threatening, or do not require hospitalisation, may be considered as an SAE when, based upon appropriate medical judgement, the event may jeopardise the participant and may require medical or surgical intervention to prevent one of the outcomes listed above.

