14.2 Trial Specific SAE Reporting requirements

In addition to the SAE reporting requirements defined in Table 7, for the purposes of this trial the following events will also be considered adverse events of special interests (AESI) and must be captured on the SAE form and reported to the CTR with 24 hours of knowledge of the event:

- Anaphylaxis and other serious hypersensitivity reactions including immune complex disease (defined by regulatory criteria of seriousness and MedDRA SMQ Hypersensitivity (Narrow)) – Grade 3 and above
- Cardiac events (i.e. cardiac ischemia, cardiac failure and thrombotic events)
- Injection site reactions (defined by MedDRA HLT Injection site reactions) grade 3 and above
- SARS-CoV-2 infections requiring hospitalisation, life threatening or death within start of treatment and 28 days following vaccine booster. Following the 28 days, reporting of these events are to be captured on the relevant eCRF.

For the purposes of this trial the following events will not require reporting as SAEs:

Hospitalisations for:

- Disease treatment
- Receipt of supportive care for disease treatment related toxicities (e.g. neutropenic sepsis, vomiting for cancer participants) (unless there is concern this has been exacerbated by vaccination)
- Disease progression (unless there is concern this has been exacerbated by vaccination)
- Pre-planned elective procedures (unless the condition worsens)
- Injection site reactions (defined by MedDRA HLT Injection site reactions) grade 2 and below
- Anaphylaxis and other serious hypersensitivity reactions including immune complex disease (defined by regulatory criteria of seriousness and MedDRA SMQ Hypersensitivity (Narrow)) – Grade 2 and below

Pre-existing conditions should only be reported if they meet the definitions for an SAE and if the condition worsens by at least one CTCAE grade.

Pre-existing conditions should be completed in the participant's notes and on the relevant toxicities CRF page and forwarded to the CTR in the normal timeframes for CRFs.

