14.5.2 CTR responsibilities

Following the initial report, all SAEs should be followed up to resolution wherever possible, and further information may be requested by the CTR. Follow up information must be provided on a new SAE form.

The CTR should continue reporting SAEs until 28 days after the participant receives their last dose of the investigational medicinal product. Serious adverse reactions should continue to be reported until the end of follow up.

Once an SAE is received at the CTR, it will be evaluated by staff at the CTR and sent to the Chief Investigator (or their delegate) for an assessment of expectedness.

Investigator reports of suspected SARs will be reviewed immediately and those that are identified as SUSARs are reported to the MHRA, Main Ethics Committee and AstraZeneca.

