16.1.6 Safety Analysis

Incidence of adverse events will be calculated as incidence rates with 95% confidence intervals. Confidence intervals will be calculated using exact Poisson methods as it is anticipated they will be relatively rare. Incidence rates will be calculated for each category of MedDRA coded preferred term (PT) and then aggregated to system organ class (SOC). In addition, serious adverse events will be categorised by PT and SOC and be presented as a detailed listing.

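### The co-primary safety outcome promises SAEs for the whole trial, but the reporting instructions end all-cause SAE reporting at about Day 56 of 180

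*Protocol*

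**What the plan says.** Section 5, Table 1, and the synopsis give the co-primary safety outcome measure as "SAE reporting throughout the trial using CTCAE V5.0". The opening of Section 14 requires all SAEs to be reported, apart from the categories exempted in Section 14.2, and sets no end date.

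Section 14.5.1 does set one. Sites report SAEs from consent "throughout the treatment period up to, and including 28 days after the participant receives their last dose of the IMP". Beyond that, serious adverse reactions (SARs) "should continue to be reported until the end of follow up as defined in the protocol". Section 14.5.2 repeats the limit for the trials unit: "The CTR should continue reporting SAEs until 28 days after the participant receives their last dose of the investigational medicinal product". Section 14.1 defines a SAR separately from an SAE, as "Any SAE occurring in a clinical trial participant for which there is a reasonable possibility that it is related to the IMP".

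Section 14.2 adds two things. SARS-CoV-2 infections that lead to hospital admission, threaten life or cause death go to an eCRF once 28 days have passed since the booster. The other AESIs, such as cardiac events, have no stated end of reporting. The section also exempts some hospital admissions from SAE reporting, for example "Disease progression (unless there is concern this has been exacerbated by vaccination").

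For the analysis, Section 16.1.6 states: "Incidence of adverse events will be calculated as incidence rates with 95% confidence intervals". It does not say what person-time goes into the denominator.

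**The concern.** A site that follows Section 14.5.1 to the letter cannot deliver the outcome in Table 1. After the cut-off, whether an event enters the SAE outcome depends mainly on a relatedness judgement. The causality table in Section 14.3 gives as examples of an unlikely relationship an event too remote in time from dosing, or one that the patient's condition explains. Late events in patients with cancer, transplants or dialysis fit both easily, so late SAEs are the ones most likely to drop out.

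The trial is open label and every participant receives AZD7442, so no untreated arm could show an excess. The all-cause count is the safety measure that depends least on judgement. An analysis plan can set the denominator, but it cannot recover events that sites were never asked to report.

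The wording in Section 14.2 is a separate and smaller matter. Its exceptions are triggered only by concern about vaccination, yet from Day 0 until the booster at Day 28 AZD7442 is the only trial product given.

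**Working it through.** Inputs, all from the protocol:

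- Both boosters are IMPs (Section 11) and are given at Day 28, plus or minus 3 days (Sections 11.1 and 13.1).
- All-cause SAE reporting ends 28 days after the last IMP dose (Sections 14.5.1 and 14.5.2).
- The final visit is Day 180, plus or minus 7 days (Section 13.1).
- Toxicity assessment and clinical review are last scheduled at Day 56 (Section 13.1 and Table 6).

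**Cut-off.** 28 + 28 = Day 56. Section 16.3 also places Day 56 at 28 days after the booster, so this reproduces the protocol's own timing.

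**Share of follow-up after dosing.** Covered: 56/180 = 31.1%. Not covered: (180 − 56)/180 = 124/180 = 68.9%.

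**Range over the visit windows.**

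- Smallest gap: booster Day 31, cut-off Day 59, final visit Day 173: (173 − 59)/173 = 65.9%.
- Largest gap: booster Day 25, cut-off Day 53, final visit Day 187: (187 − 53)/187 = 71.7%.

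**No booster given.** The last IMP dose is then Day 0 and the cut-off is Day 28: (180 − 28)/180 = 84.4% not covered.

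**Person-time.** If all 350 planned participants were followed to Day 180 (an assumption), all-cause reporting would cover 350 × 56 = 19,600 of 350 × 180 = 63,000 person-days.

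**Effect on a rate if the denominator does not match.** With a constant rate r per day, about 56r SAEs per participant are counted. Dividing by 180 days gives 0.311r, an understatement of 180/56 = 3.2-fold. This is an upper figure at the nominal days. It falls if SARs or AESIs after Day 56 are counted or if participants leave early, and it disappears if person-time stops at the cut-off.

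**Exposure, as context only.** Section 4.6 reports: "The half-life of AZD7442 is estimated to be ~ 90 days". Under simple exponential decline from Day 0, the fraction left is 2^(−56/90) = 0.65 at Day 56 and 2^(−180/90) = 0.25 at Day 180.

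**The case against.** The strongest case on the other side has five parts.

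- **The window is legitimate.** Reporting SAEs to 28 days after the last dose and SARs to the end of follow-up is not an error in itself. A SAR is by definition an SAE, so some SAE reporting does run throughout. This stands as a defence of the window. It does not reconcile the window with Table 1, because the protocol defines the two terms separately.
- **Late capture is not confined to related events.** A reader might infer that after Day 56 nothing but related events is recorded. The documents do not support that: severe or fatal SARS-CoV-2 infections still go to an eCRF, the other AESIs have no stated end, and safety bloods are taken at Day 180. The relatedness filter is also broad, since a possible relationship counts and the site's judgement cannot be downgraded. All of this stands, but none of it restores general SAE reporting.
- **The 3.2-fold figure is hypothetical.** A reader might infer that reported rates will be that far too low. Section 16.1.6 names no denominator, and person-time is commonly left to the analysis plan. The figure shows only what a mismatch would do.
- **The exposure figures are borrowed.** The half-life comes from a Phase I study in healthy volunteers. The 65% and 25% are rough and say nothing about whether late harm occurs.
- **Full collection has a price and may be hard to interpret.** Each extra event needs its own form, causality review and follow-up. Without a control arm, late SAEs would largely reflect underlying disease. Recruitment was paused in April 2023, before this version of the protocol, so some collection might be retrospective. This stands, and it is why full collection is optional in the fix.

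**Conclusion.** The contradiction is real and lies wholly within the protocol. Table 1, the synopsis and the opening of Section 14 set no early end to SAE reporting; Sections 14.5.1 and 14.5.2 end all-cause reporting at about Day 56, or about Day 28 without a booster. No other section resolves this, and the schedule of toxicity assessments agrees with the early stop.

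The gap is 124 of 180 days, 69%, with a range of 66% to 72% over the visit windows. This takes the whole trial to mean dosing to the Day 180 visit and leaves out the interval between consent and dosing. In that gap, unrelated SAEs and non-COVID deaths are not required to be reported as SAEs. The understatement of up to 3.2-fold is conditional on a constant rate and a mismatched denominator. The fault is the conflict with the declared co-primary outcome, not the choice of a 28-day window.

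**What to change.** Reconcile the sections in one of two ways.

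- **Minimum.** In Table 1 and the synopsis, restate the outcome as *all SAEs from consent to 28 days after the last IMP dose, and SARs to Day 180*. Add the same limit to the opening of Section 14. In Section 16.1.6, end person-time for all-cause SAE rates at that cut-off. In Section 14.2, state when AESI reporting ends. This costs wording only.
- **Alternative.** Keep the outcome as it stands and extend Sections 14.5.1 and 14.5.2 to Day 180, asking about SAEs at the existing Day 112 and Day 180 visits. No visit is added, but each further event brings an SAE form, causality reviews and follow-up, and part of the collection may be retrospective.

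Under either choice, extend the exceptions in Section 14.2 that now mention only vaccination so that they also cover AZD7442. This too is a change of wording.

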14.5.2 CTR responsibilities

Following the initial report, all SAEs should be followed up to resolution wherever possible, and further information may be requested by the CTR. Follow up information must be provided on a new SAE form.

The CTR should continue reporting SAEs until 28 days after the participant receives their last dose of the investigational medicinal product. Serious adverse reactions should continue to be reported until the end of follow up.

Once an SAE is received at the CTR, it will be evaluated by staff at the CTR and sent to the Chief Investigator (or their delegate) for an assessment of expectedness.

Investigator reports of suspected SARs will be reviewed immediately and those that are identified as SUSARs are reported to the MHRA, Main Ethics Committee and AstraZeneca.

